3.4.2 Safety endpoints

Adverse events

AEs will be coded using the most recent version of the Medical Dictionary for Regulatory Activities.

A treatment emergent adverse event (TEAE) is defined as an event that has onset date on or after the first day of IMP administration and no later than seven days after the last day on IMP. If the event has onset date before the first day of IMP administration and increases in severity during the treatment period and until 7 days after the last drug date, then this event should also be considered as a TEAE. Here the first day of IMP administration is defined as the first day of exposure to liraglutide.

AEs will be summarised descriptively for each of the following periods separately:

- The run-in period: TEAEs with an onset date on or after the first day of exposure to liraglutide and before the date of randomisation will be reported as part of the run-in period. For the run-in failure subjects, AEs with an onset date on or after the first day of exposure to liraglutide and no later than seven days after the last day of liraglutide treatment will be reported as part of the run-in period.
- The 26 week treatment period: TEAEs with an onset date on or after the date of randomisation and no later than seven days after Visit 16 (EOT26) will be reported as during 26 weeks of treatment. For subjects in the liraglutide 0.9 mg arm as well as for subjects in both arms who withdrew from the trial during 26 weeks of treatment, TEAEs with an onset date on or after the date of randomisation and no later than seven days after the last day of liraglutide treatment will be reported as part of 26 weeks of treatment.
- The 52 week treatment period: For the liraglutide 1.8 mg arm all TEAEs with an onset date on or after the date of randomisation will be reported as during 52 weeks of treatment.

For each of the above periods, AE data will be displayed in terms of the number of subjects with at least one event (N), the percentage of subjects with at least one event (%), the number of events (E) and the event rate per 100 years of exposure (R).

Summaries of AEs and of serious AEs will be presented as an overview including all AEs, serious AEs, number of deaths, AEs by severity, AEs by relation to treatment and AEs of special interest including AEs leading to withdrawal for each period.

Furthermore separate summary tables for each period will be presented based on system organ class and preferred terms for:

- All AEs
- Serious AEs

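### Adverse events are assigned to periods by onset date only, so a run-in event that worsens, becomes serious or causes withdrawal after randomisation is absent from the 26- and 52-week tables

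*SAP*

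**What the plan says.** The rules are in SAP Section 3.4.2, under adverse events.

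- **Run-in rule:** "TEAEs with an onset date on or after the first day of exposure to liraglutide and before the date of randomisation will be reported" under this heading.
- **26-week period, general rule:** "TEAEs with an onset date on or after the date of randomisation and no later than seven days after Visit 16 (EOT26) will be reported" under the 26 weeks.
- **26-week period, for the 0.9 mg arm and for anyone who withdrew in those weeks:** the window closes differently but opens at the same point: "TEAEs with an onset date on or after the date of randomisation and no later than seven days after the last day of liraglutide treatment".
- **52-week rule:** "For the liraglutide 1.8 mg arm all TEAEs with an onset date on or after the date of randomisation will be reported as during 52", the unit being weeks.
- **Worsening:** an older event can become treatment emergent: "If the event has onset date before the first day of IMP administration and increases in severity during the treatment period". The reference day is then fixed: "Here the first day of IMP administration is defined as the first day of exposure to liraglutide". That day lies in the run-in, before randomisation.
- **Overview tables:** these cover severity, seriousness and "AEs of special interest including AEs leading to withdrawal for each period". No rule uses the date of withdrawal, the date of a severity change or the date an event became serious.

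Section 2.2.2 lists the number of treatment-emergent adverse events during 26 weeks as a secondary safety endpoint chosen for disclosure. Section 1.1 gives the comparison of safety between the two doses as part of the trial's purpose.

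**The concern.** The doses separate at randomisation, but the SAP's worsening clause acts only at the first liraglutide dose. An event already ongoing at randomisation can change on the randomised dose in three ways that matter for safety: it can worsen, become serious or end the subject's participation. Each change happens under the treatment being compared, yet the event is filed by the day it began.

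Withdrawal is the clearest case. A subject who leaves at week 3 of randomised treatment because of nausea that began in the run-in would appear as a run-in event leading to withdrawal. The 26-week overview, which is where a reader compares the arms on tolerability, would not show that withdrawal as due to an adverse event.

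**Working it through.** The plan states no figure on this point, so the check is to apply its rules to test events. Day 0 is randomisation. First liraglutide is day −F, with F assumed to be 14 or 84 days because the SAP does not give the run-in length. Week 26 is day 26 × 7 = 182 and week 52 is day 52 × 7 = 364.

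Rules as conditions on the onset day *t*:

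1. Treatment emergent: −F ≤ *t* ≤ last dose + 7; or *t* < −F with worsening between −F and last dose + 7.
2. Run-in: −F ≤ *t* < 0.
3. 26 weeks: 0 ≤ *t* ≤ 182 + 7 = 189; or 0 ≤ *t* ≤ last dose + 7 for the 0.9 mg arm and for subjects who withdrew.
4. 52 weeks (1.8 mg arm only): *t* ≥ 0.

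| Test event | 0.9 mg arm | 1.8 mg arm |
|---|---|---|
| Onset day −5, worsens day 10 | run-in only | run-in only |
| Onset day −5, worsens day 10, withdrawn day 20 | run-in only | run-in only |
| New onset day 10 | 26 weeks | 26 and 52 weeks |
| Onset before liraglutide (day −F − 5), worsens day 10 | treatment emergent, no period | treatment emergent, no period |

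In the first two rows *t* = −5 satisfies rule 2 and fails the lower limit of 0 in rules 3 and 4. For the withdrawn subject the 26-week window is 0 to 20 + 7 = 27, and −5 is still outside it. The worsening part of rule 1 is not used, because −5 is not earlier than −F. Results are the same for F = 14 and F = 84.

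The last row is a separate gap in the same rules: such an event is treatment emergent but meets no period's onset condition.

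**Illustration of size; every input is assumed.** Let *q* be the share of subjects randomised with an ongoing run-in event and *w* the share of those whose event then worsens. The uncounted outcomes per 100 subjects in an arm are 100 × *q* × *w*.

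- Low: *q* = 5%, *w* = 5%: 100 × 0.05 × 0.05 = 0.25.
- High: *q* = 20%, *w* = 30%: 100 × 0.20 × 0.30 = 6.0.

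The uncounted difference between arms is 100 × *q* × (difference in *w*).

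- Equal *w* in both arms: 0.
- *q* = 5%, *w* of 5% and 15%: 100 × 0.05 × 0.10 = 0.5.
- *q* = 20%, *w* of 10% and 30%: 100 × 0.20 × 0.20 = 4.0.

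Nothing in the SAP says which arm has the larger *w*.

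**The case against.** **Recording of worsened events may close part of the gap.** Whether a worsened event becomes a new record with its own onset date is commonly a protocol matter, and the protocol is not at hand. If it does, worsening after randomisation gets a post-randomisation onset and is counted. This stands as a limit. It does not dispose of the point: an event that leads to withdrawal without a new record would still be filed under the run-in. The SAP's one sentence on recording deterioration belongs to the physical examination paragraph, concerns pre-existing conditions and gives no onset or period rule.

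**Onset-based allocation is defensible.** It gives each event one place and avoids double counting. Section 4 explains that the reference day is liraglutide exposure so as to match the safety analysis set. This also stands: the event did begin in the run-in and belongs in that count, so the run-in event count is not inflated. What is misplaced is the later severity, seriousness or withdrawal.

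**Stronger readings that the SAP does not support.**

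- A reader might infer that the 26-week comparison misses harm caused by a step up to 1.8 mg, and so understates the difference between doses. New-onset events after randomisation are counted, and the SAP does not state the run-in dose. Neither a step nor a direction of bias can be read from it.
- A reader might set the omitted outcomes against the 5% display threshold. That threshold applies to each preferred term, whereas the illustrated totals run over all terms. The table of all adverse events has no threshold, so no term is hidden.
- The totals are not subjects lost from the tables. A subject with any other post-randomisation event still counts in the overall number with at least one event.

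**Conclusion.** The point holds in a limited form. On the SAP's wording, a worsening, a change to serious or a withdrawal that occurs on or after randomisation, arising from an event that began in the run-in, is absent from the by-arm 26-week tables and, for 1.8 mg, from the 52-week tables. Nothing else in the SAP repairs this.

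Size and direction are not derivable from the document. The illustrated 0.25 to 6.0 per 100 subjects per arm rests wholly on assumed rates and covers worsening, the part that vanishes under new recording. The adverse event summaries are descriptive, so no test, error rate or superiority conclusion is touched. The consequence is an incomplete tolerability comparison in a set of safety results that includes a disclosed endpoint. It is worth correcting because the correction is cheap.

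**What to change.** In SAP Section 3.4.2:

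1. Assign adverse events leading to withdrawal to the period in which the withdrawal occurred.
2. Add a by-arm summary, or a footnoted count, for the 26-week period and for the 52-week period in the 1.8 mg arm. It should show run-in-onset treatment-emergent events that, on or after randomisation, increase in severity, become serious or lead to withdrawal.
3. Leave the onset-based event counts and rates as they are, so that onset and worsening are not mixed in one rate.
4. If the protocol has worsened events recorded as new ones with their own onset date, say so in one sentence. The summary in item 2 can then be limited to events without a new record.

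The cost is SAP wording and modest programming. Some events will appear in two tables and need a footnote. Where severity changes are not dated, only the dates of seriousness and withdrawal can be used, and the table should state this.

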1.1 Trial information

This is a 26-week randomised, parallel, two-arm, open-label, multi-centre trial comparing the efficacy and safety of liraglutide 1.8 mg/day to liraglutide 0.9 mg/day in Japanese subjects with T2DM. The liraglutide 1.8 mg/day treatment arm will be continued for a total of 52 weeks after randomisation for monitoring of safety and glycaemic control over 52 weeks. Refer to the protocol for further details.

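### The 26-week AE tables select events by onset alone, so an AE leading to withdrawal after week 26 can count there for 1.8 mg, with no counterpart for 0.9 mg

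*SAP*

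**What the plan says.** SAP section 1.1 describes the design: "This is a 26-week randomised, parallel, two-arm, open-label, multi-centre trial". It adds that "The liraglutide 1.8 mg/day treatment arm will be continued for a total of 52 weeks after randomisation". The 0.9 mg arm has no treatment period after week 26.

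SAP section 3.4.2 (Adverse events) sets the reporting periods, and onset date is the only allocation rule:

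- **26 weeks, general rule:** "TEAEs with an onset date on or after the date of randomisation and no later than seven days after Visit 16 (EOT26").
- **26 weeks, 0.9 mg arm and early withdrawals in either arm:** onset from randomisation and "no later than seven days after the last day of liraglutide treatment will be reported as part of 26 weeks of treatment".
- **52 weeks:** "For the liraglutide 1.8 mg arm all TEAEs with an onset date on or after the date of randomisation". No 52-week table exists for 0.9 mg.

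The overview tables for each period then report what became of these events: "number of deaths, AEs by severity, AEs by relation to treatment and AEs of special interest including AEs leading to withdrawal for each period". No date is fixed by which a withdrawal or a death must have occurred to be shown in the 26-week table. The tables are descriptive: "AEs will be summarised descriptively for each of the following periods separately".

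**The concern.** An event's onset and the withdrawal it causes are two dates, and the SAP restricts only the first. In the 0.9 mg arm the second date is limited by design, because treatment ends at week 26. In the 1.8 mg arm an event with onset inside the window has about 26 further weeks on treatment in which it can lead to withdrawal. If the table is programmed from the final database with the onset rule alone, those later withdrawals are shown under 26 weeks.

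The 26-week tables are the SAP's only between-dose comparison of adverse events, and withdrawal because of an AE is a natural tolerability measure for comparing two doses. Unequal time for an event to end in withdrawal would make 1.8 mg look less well tolerated for a reason unrelated to the first 26 weeks. SAP section 4 also acknowledges that statisticians and programmers are hard to keep blinded before database lock, so the cut-off is better written down than left to programming.

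**Working it through.** The SAP gives no AE or withdrawal rates, so there is no figure of its own to reproduce. The check is a reading of the rules, then an illustration of size.

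**Step 1: follow one event through the rules.** Take an AE with onset in week 20 that leads to withdrawal in week 35.

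- *1.8 mg:* the onset precedes Visit 16 + 7 days, so the event is in the 26-week set. It led to withdrawal, and no rule removes it from that line of the table. It counts.
- *0.9 mg:* treatment ended at week 26, so there is no withdrawal in week 35. The case cannot arise.

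An AE with onset later than Visit 16 + 7 days is excluded from the 26-week table by the onset rule, whatever follows. The problem is therefore confined to in-window onsets with a later withdrawal.

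**Step 2: how much further time each arm has.** From the SAP: treatment for 26 weeks (0.9 mg) and 52 weeks (1.8 mg), and a 7-day margin. Assumed: in-window onsets uniform over weeks 0 to 27, and observation ending at week 27 (0.9 mg) or week 53 (1.8 mg).

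- 0.9 mg: mean time after onset = 27/2 = 13.5 weeks (range 0 to 27).
- 1.8 mg: mean time after onset = 53 − 27/2 = 39.5 weeks (range 26 to 53).

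**Step 3: share of eventual withdrawals captured.** Assume also that the lag from onset to withdrawal is exponential with mean m weeks, the same in both arms.

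- 0.9 mg: 1 − (m/27)(1 − exp(−27/m))
- 1.8 mg: 1 − (m/27)(exp(−26/m) − exp(−53/m))

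| Mean lag m (weeks) | 0.9 mg | 1.8 mg | Ratio |
|---|---|---|---|
| 1 | 96% | 100% | 1.04 |
| 2 | 93% | 100% | 1.08 |
| 4 | 85% | 100% | 1.17 |
| 8 | 71% | 99% | 1.39 |
| 13 | 58% | 94% | 1.63 |
| 26 | 38% | 77% | 2.04 |

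**Step 4: percentage points.** Added points in the 1.8 mg arm = (share of the arm withdrawing for an AE in weeks 27-52) × (share of those AEs with in-window onset). Assume the first factor is 2% to 4%.

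The second factor follows from the same lag model if onsets stay uniform to week 53. Withdrawals after week 27 from in-window onsets are proportional to A = m(1 − exp(−27/m)) − m(exp(−26/m) − exp(−53/m)). Those from later onsets are proportional to B = 26 − m(1 − exp(−26/m)). The share is A/(A + B).

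- m = 1: 1.0/(1.0 + 25.0) = 4%. m = 2: 2.0/(2.0 + 24.0) = 8%. m = 4: 3.99/(3.99 + 22.01) = 15%.
- A share of 20% needs a mean lag of about 5 weeks, and 50% needs about 22 weeks.

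Short lags (1 to 4 weeks): from 0.02 × 0.04 = 0.08 points to 0.04 × 0.15 = 0.6 points. Longer lags (about 5 to 22 weeks): from 0.02 × 0.20 = 0.4 points to 0.04 × 0.50 = 2.0 points.

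**Step 5: effect of a common cut-off.** If withdrawals are cut at the end of the same window as onsets in both arms, both follow the first formula and the ratio is 1.00 at any lag.

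**The case against.** The strongest reply is that the SAP never says later withdrawals count. Showing AEs leading to withdrawal for each period could mean withdrawals that happen in that period. This is fair: the rule is unfixed, not wrongly stated, and the point has to say *can count*. But onset is the only period rule given, so the reading that needs no added assumption is the one that lets later withdrawals in.

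A reader might go further and infer that deaths, seriousness and worsening in weeks 27-52 are also loaded onto the 1.8 mg arm alone. The document does not support that. A 0.9 mg event can still become serious or fatal after treatment ends, and section 3.4.2 plans a listing of AEs collected after the treatment-emergent period, so collection does not stop there. How long outcomes are followed, and whether severity is recorded as a maximum over the event, may be set in the protocol, which is not at hand. Deaths may equally be assigned by date of death.

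It is also true that the tables are descriptive, that withdrawal because of an AE is not a listed endpoint, and that the disclosed 26-week TEAE count depends on onset and does not move. Finally, if most AEs that lead to withdrawal do so within a few weeks, the effect is small. All of this stands and limits the weight of the point. None of it supplies the missing date.

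**Conclusion.** The point holds for AEs leading to withdrawal, restricted to events with onset by Visit 16 + 7 days. For that item the direction is certain: the onset-only rule can add withdrawals to the 1.8 mg arm and never to the 0.9 mg arm.

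The size is not known. The capture ratios and percentage points rest wholly on assumed onset patterns, lags and withdrawal rates. They show a small effect for short lags and a material one only where events persist for months before withdrawal. Counts and rates of all TEAEs are untouched. This is an inexpensive improvement to a descriptive comparison and does not call the primary result into question.

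**What to change.** Add to SAP section 3.4.2, Adverse events, after the period definitions:

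> *In the 26-week tables an AE is counted as leading to withdrawal only if the withdrawal occurred by the end of the subject's 26-week AE window: seven days after Visit 16, or seven days after the last liraglutide dose for the 0.9 mg arm and for subjects withdrawn before Visit 16. Deaths are assigned to a period by date of death, with the same cut-off in both arms. Later withdrawals and deaths from AEs with onset in the window are listed for both arms and, for 1.8 mg, included in the 52-week tables.*

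State also which date serves as the withdrawal date. For a subject withdrawn before Visit 16, a formal withdrawal recorded more than seven days after the last dose should not drop out of the 26-week table through an administrative delay.

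Leave severity and seriousness as recorded, with a footnote that follow-up after week 26 differs by arm. Truncating them would depend on changes that may be undated. The listing must cover both arms, because the 52-week tables exist for 1.8 mg only and a late outcome in a 0.9 mg subject would otherwise appear in no output under this rule.

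The cost is one date condition in the table programs, one extra listing and a footnote. No new data should be needed, since withdrawal and death dates should already be in the database.
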